OBJECTIVES	
Primary Objective: To determine the anti-tumor efficacy of brentuximab vedotin in relapsed/refractory NSGCT.
 
Secondary Objectives:
 
 1) To determine the progression free survival in patients with relapsed/refractory NSGCT treated with brentuximab vedotin. 2) To determine the overall survival of patients with relapsed/refractory NSGCT treated with brentuximab vedotin. 3) To determine the safety and tolerability of brentuximab vedotin in this patient population. 
Exploratory Objectives:
 
 1) To characterize the intensity and localization (cell wall vs. cytoplasmic) of CD30 staining among tumors from patients with relapsed or refractory NSGCT enrolling on the study. 2) To correlate the intensity and localization of tumor staining for CD30 with objective response and progression-free survival for patients enrolling on the study.
STUDY DESIGN	Phase II study with 2 cohorts in parallel using a Simon two-stage design
ELIGIBILITY CRITERIA	
Main Inclusion Criteria:
 
 1. Age \geq 18 years at the time of screening. 2. Patients with histologically or serologically confirmed relapsed/refractory non-seminoma germ cell tumor, (i.e. embryonal carcinoma, choriocarcinoma, or yolk sac tumors) including female GCT and primary mediastinal NSGCT. 3. Patients must have progressed after prior high dose chemotherapy (HDCT) treatment, been deemed not to be a candidate for high dose chemotherapy or refused high-dose chemotherapy, and be considered incurable by other standard therapies including further chemotherapy or surgery. There is no maximum allowable number of previous therapies.

	
 4. Patients with measurable disease according to RECIST v1.1, or with rising AFP or BHCG above the upper limit of normal on two consecutive determinations if no measurable radiologic disease. 5. Patients with brain metastases are allowed onto the study as long as patients have completed their treatment for brain metastasis, no longer require corticosteroids, and are asymptomatic. Subjects with neurological symptoms should undergo a head CT scan or brain MRI to exclude brain metastasis, at the discretion of the treating physician. 6. Patients with ECOG performance status of 0-2. 7. Adequate organ and marrow function as detailed in the protocol. 8. Patients who are willing and able to comply with the protocol and study procedures including willingness to undergo tumor biopsy for tumor cells before therapy to assess for CD30 status (unless archival tumor tissue from orchiectomy or other previous sample is not obtainable despite efforts to do so and a fresh tumor biopsy is not feasible). 
Main Exclusion Criteria:
 
 1. Patients with pure seminoma. 2. Patients with pure teratoma. 3. Chemotherapy within 2 weeks of initiating study treatment. 4. Major surgery within 3 weeks of starting study treatment. There is no minimum time requirement for minor procedures such as biopsy or vascular access placement. 5. Radiation within 2 weeks of starting study treatment. 6. \geq Grade 3 neuropathy at the time of enrollment. 7. Pregnancy or breast-feeding. 8. Previous treatment with any anti-CD30 directed therapy.

STATISTICAL CONSIDERATIONS
	
a) Definition of primary outcome/endpoint:
 
Objective response rate is the proportion of patients who achieve either a partial or complete response.
 
Complete response is defined as disappearance of all target lesions and normalization of serum tumor markers (AFP and beta-hCG) for at least 4 weeks. Any pathological lymph nodes (whether target or non-target) must have reduction in short axis to <10 mm. Complete Response must be confirmed four or more weeks after initial CR is observed.
 
In patients whose only evidence of disease is elevated serum tumor markers (AFP or beta-hCG), then values must fall below the upper limit of normal for the assay employed and remain at that level for at least 4 weeks.
 
Partial response is defined as at least a 30% decrease in the sum of the diameters of target lesions, taking as reference the baseline sum diameters. This should be present on at least 2 measurements 1 month

apart. The serum tumor markers (AFP and beta-hCG) should be stable or decreasing. Partial Response must be confirmed four or more weeks after initial PR is observed.

In patients whose only evidence of disease is elevated serum tumor markers (AFP or beta-hCG), then values must fall $\geq 90\%$ below baseline pretreatment levels for beta-hCG or 50% decrease below baseline pretreatment levels for AFP and persist for 6 weeks. If both tumor markers are elevated and one falls below 90% the other should fall at least below 50% of baseline pretreatment levels.

b) Definition of secondary outcomes/endpoints:

Progression-free survival (PFS) time is the time measured from the date of initiation of therapy until disease progression or death, whichever comes first. Patients alive and progression-free will be censored at their last follow-up.

Overall survival (OS) is the time measured from the date of initiation of therapy until death, regardless of cause. Patients alive at the time of data analysis will be censored at their last date of contact.

c) Analytic plan for primary objective:

The ORR and its 95% exact CI will be summarized for the total population and by cohort using the F distribution method (Collett 1991).

d) Analytic plan for secondary objectives:

- Both PFS and OS will be estimates using the methods of Kaplan and Meier for each cohort separately.
- Toxicities will be assessed based on the Common Terminology Criteria for Adverse Events (CTCAE) version 4.0. The maximum grade of each toxicity will be recorded for each patient over the course of treatment (all cycles). Toxicities will be recorded up until 30 days after the last day of treatment. The incidence of treatment delays, dose reductions, and early discontinuations of treatment due to toxicity or patient choice, will also be recorded as a means of assessing the tolerability of treatment for each cohort.
- CD30 staining will be characterized by intensity (0 to 3+) and by localization (cell wall vs. cytoplasmic) and correlated with response using logistic regression and with PFS using proportional hazards regression.

e) Sample size justification:

An optimal Simon two-stage design will be used for each cohort of patients to differentiate between the null hypothesis that the response rate P is $\leq 5\%$ ($P \leq 0.05$) and the alternative hypothesis that the response rate is $\geq 20\%$ ($P \geq 0.20$). Under this design, the probability of

[figure not shown]
	
early termination under the null hypothesis is 0.599. This design yields a type I error rate, α (probability of concluding that the drug is not effective when it is actually effective) of 0.047 and a power of 0.801 (type II error rate 0.199) when the true response rate is $\geq 20\%$. In the first stage in each cohort, 10 patients will be enrolled. If there are no objective responses, then that cohort will terminate. If ≥ 1 response is observed, then an additional 19 patients will be enrolled in the second stage for a total sample size of 29 patients per cohort. If 3 or fewer responses are observed out of the 29 patients, then brentuximab vedotin will be declared as not worthy of further study. If ≥ 4 objective responses are achieved, then brentuximab vedotin will be deemed active in refractory/relapsed NSGCT and worthy of further study.
 
f) Accrual estimation: We estimate enrolling 2 patients/month for the CD30 negative cohort and 1 patient/month for the CD30 positive patients.

TOTAL NUMBER OF SUBJECTS	N = 58 (10 patients in the first stage + 19 patients in the second stage= 29 per cohort x 2 cohorts)
ESTIMATED ENROLLMENT PERIOD	Estimated 24 months
ESTIMATED STUDY DURATION	Estimated 36 months

TABLE OF CONTENTS

Schema.....	9
1. Background and Rationale.....	10
1.1 Relapsed and Refractory Germ Cell Tumors.....	10
1.2 Current Standard of Care	10

1. BACKGROUND AND RATIONALE

1.1 Relapsed and Refractory Germ Cell Tumors

Germ cell tumors (GCT) are the most common malignancies among men between ages 15 and 35. In 2013, 7,920 cases and 370 deaths were estimated to occur in the United States.(1) Cisplatin-based chemotherapy has transformed this disease from the most common cause of cancer death among young men to a model of curative malignancy.(2) Patients who are not cured with initial platinum-based chemotherapy are usually treated with salvage chemotherapy. Approximately 50% of these testicular cancer patients will subsequently be cured with salvage chemotherapy with tandem transplant of high-dose chemotherapy with peripheral stem cell rescue. Today, with modern chemotherapy and surgery techniques, 80-90% of patients will survive their disease. For the unfortunate 10-20% who are not cured by these measures, there is a desperate need for novel therapeutic agents.

Germ cell tumors of the ovary are very rare. Relapsed ovarian GCT after chemotherapy carries a poor prognosis and there are very few trials that looked at novel therapies for this disease.(3)

1.2 Current Standard of Care

Seven phase 2 clinical trials evaluated single-agents activity in 90 refractory GCT patients at MSKCC showed median progression free survival (PFS) of 4 weeks and median overall survival (OS) of 4 months.(4) Similar experience at Indiana University (IU) showed that chemotherapy post-HDCT result in a response rate of less than 20%, with a median survival time of 8 months. All deaths occurred within 12 months of HDCT.(5) An average of more than 35 years of life is lost when a patient dies from GCT, well over a decade longer than any other adult malignancy. Therefore, there is currently no standard of care for patients who relapse after high-dose chemotherapy and have no surgically resectable disease. The development of novel treatment options for this patient population is needed.

1.3 Brentuximab Vedotin

Brentuximab vedotin (SGN-35 or ADCETRIS) is an antibody-drug conjugate (ADC) consisting of 3 components: 1) the antibody cAC10, specific for human CD30; 2) the potent antimicrotubule agent monomethyl auristatin E (MMAE); and 3) a protease-cleavable linker that covalently attaches MMAE to cAC10. The biological activity of brentuximab vedotin results from a multi-step process. Binding of the ADC to CD30 on the cell surface initiates internalization of the ADC-CD30 complex, which then traffics to the lysosomal compartment. Within the cell, a single defined active species, MMAE, is released via proteolytic cleavage. Binding of MMAE to tubulin disrupts the microtubule network within the cell, induces cell cycle arrest, and results in apoptotic death of the CD30-expressing tumor cell. Contributions to the mechanism of action by other antibody-associated functions have not been excluded.(6)

1.3.1 Experience with Brentuximab Vedotin

To date, more than 700 patients have received brentuximab vedotin in 10 completed

clinical studies.

Two phase 2 studies evaluating the efficacy and safety of brentuximab vedotin as a single agent have been performed in patients with relapsed or refractory Hodgkin lymphoma (HL; Study SG035-0003) and systemic anaplastic large cell lymphoma (ALCL; Study SG035-0004). The objective response rate (ORR) for HL patients was 75%, with approximately one-third of patients achieving a complete response/remission (CR) (Seattle Genetics, Clinical Study Report No. SG035-0003, 2010). ALCL patients had an ORR of 86%, with over 50% of patients achieving a CR (Seattle Genetics, Clinical Study Report No. SG035-0004, 2010). In both studies, brentuximab vedotin was generally well tolerated with manageable side effects.

A complete summary of the clinical and nonclinical data relevant to the investigational product and its study in human subjects is provided in the Investigator's Brochure.

Brentuximab vedotin is currently FDA-approved in relapsed or refractory Hodgkin's lymphoma and relapsed or refractory systemic anaplastic large cell lymphoma.

visual central review was 25% in the responders vs. 25% in the nonresponders. Twenty-one percent of the responders had <10% CD30 expression. Two patients with DLBCL with ≤1% detectable CD30 expression by central pathologist review achieved CR. Although the precise mechanisms underlying this phenomenon remain unknown, some evidence indicates a 'bystander effect', whereby free MMAE is released from dying cells in concentrations sufficient to kill neighboring tumor cells(17) either directly or indirectly by altering the tumor microenvironment.(18)

Patients will be enrolled into two cohorts, one for CD30 positive patients and one for CD30 negative (or CD30 unknown). CD30 status may be unknown in the unlikely case of tumor-marker-only relapse or when a fresh tumor biopsy is not feasible, and archival tumor tissue is not obtainable despite efforts to do so. We would like to enroll such patients if they are otherwise eligible for the study and would include them in the CD30 negative cohort for analysis purposes, since statistically NSGCT are more likely to be CD30 negative. **The number of such patients with unknown CD30 status should not exceed 5 patients.**

2. STUDY OBJECTIVES AND ENDPOINTS

2.1 Objectives

2.1.1 Primary Objective

To determine the anti-tumor efficacy of brentuximab vedotin in relapsed/refractory NSGCT.

2.1.2 Secondary Objectives

- 1) To determine the progression free survival in patients with relapsed/refractory NSGCT treated with brentuximab vedotin.
- 2) To determine the overall survival of patients with relapsed/refractory NSGCT treated with brentuximab vedotin.
- 3) To determine the safety and tolerability of brentuximab vedotin in this patient population.

2.1.3 Correlative/Exploratory Objectives

- 1) To characterize the intensity and localization (cell wall vs. cytoplasmic) of CD30 staining among tumors from patients with relapsed or refractory NSGCT enrolling on the study.
- 2) To correlate the intensity and localization of tumor staining for CD30 with objective response and progression-free survival for patients enrolling on the study.

2.2 Endpoints

2.2.1 Primary Endpoint

Objective response (CR + PR) measured by RECIST Criteria v1.1 if there is measurable disease. In case of no measurable disease (marker-only patients), response can be assessed by either a reduction of BHCG by >90% (with no rise in AFP on two

consecutive measures) or a reduction of AFP by >50% (with no rise in BHCG on two consecutive measures).

2.2.2 Secondary Endpoints

1. Progression-free survival time defined from the start of the treatment until death, criteria for disease progression are met, or last follow-up visit. Overall survival time defined from the start of the treatment until death or last follow-up visit.
2. Toxicity measured by Common Toxicity Criteria 4.0 and need for treatment delay, dose reduction, or early discontinuation.
3. Correlation between tumor CD30 staining intensity/localization and objective response and progression-free survival.

3. ELIGIBILITY CRITERIA

3.1 Inclusion Criteria

Subject must meet all of the following applicable inclusion criteria to participate in this study:

1. Age \geq 18 years at the time of informed consent.
2. Patients with histologically or serologically confirmed relapsed/refractory non-seminoma germ cell tumor, (i.e., embryonal carcinoma, choriocarcinoma, or yolk sac tumors) including female GCT and primary mediastinal NSGCT.
3. Patients must have progressed after prior high dose chemotherapy (HDCT) treatment, been deemed not to be a candidate for high dose chemotherapy or refused high-dose chemotherapy, and be considered incurable by other standard therapies including further chemotherapy or surgery. There is no maximum allowable number of previous therapies.

“Failure” of prior therapy is defined as:

- a. A >25% increase in the products of perpendicular diameters of measurable tumor masses during prior therapy which are not amenable to surgical resection.
- b. The presence of new tumors which are not amenable to surgical resection.
- c. An increase in AFP or beta-hCG (two separate determinations at least one week apart are required if rising tumor markers are the only evidence of failure).

NOTE: Patients with clinically growing “teratoma” (normal declining tumor markers and radiographic or clinical progression) should be considered for surgery.

4. Patients must have evidence of recurrent or metastatic carcinoma by one or more of the following:
 - i) The appearance of metastatic disease by standard imaging techniques
 - ii) The appearance of rising serum tumor marker, AFP or beta-hCG

- NOTE:** If a rising tumor marker is the only evidence of progressive disease, at least 2 consecutive rising values at least one week apart are needed. Patients with only evidence of disease is rising tumor marker AFP and beta-hCG will be provided alternate causes of increased serum levels of these markers are not present, such as cross reaction with luteinizing Hormone (LH) (that can be tested if needed by testosterone suppression of LH), hepatitis, use of marijuana or second primary tumor, etc.
5. Patients with primary medistinal non seminomatous germ cell tumor are eligible if they have received first line platinum based chemotherapy and their recurrence is not amenable to surgical resection based on the treating physician expert opinion.
 6. Patients with late relapse (>2 years) of non seminomatous germ cell tumors are eligible if they have received first line platinum based chemotherapy and their recurrence is not amenable to surgical resection based on the treating physician expert opinion.
 7. Patients with brain metastases are allowed onto the study as long as patients have completed their treatment for brain metastasis, no longer require corticosteroids, and are asymptomatic. Subjects with neurological symptoms should undergo a head CT scan or brain MRI to exclude brain metastasis, at the discretion of the treating physician.
 8. Patients with ECOG performance status of 0-2.
 9. Adequate organ and marrow function as defined below:
 - a. Hemoglobin ≥ 8 g/dL
 - b. Absolute neutrophil count $\geq 1,000/\text{mm}^3$
 - c. Platelet count $\geq 75,000/\text{mm}^3$
 - d. Total bilirubin $\leq 1.5 \times \text{ULN}$ except patients with documented Gilbert's syndrome ($\leq 3 \times \text{ULN}$)
 - e. Alanine aminotransferase (ALT) and aspartate aminotransferase (AST) $\leq 2.5 \times \text{ULN}$; for patients with hepatic metastases, ALT and AST $\leq 5 \times \text{ULN}$
 - f. Calculated creatinine clearance ≥ 30 mL/min as determined by the Cockcroft-Gault equation.
 10. Patients who are willing and able to comply with the protocol and study procedures including willingness to undergo tumor biopsy for tumor cells before therapy to assess for CD30 status (unless archival tumor tissue from orchiectomy or other previous sample is not obtainable despite efforts to do so and a fresh tumor biopsy is not feasible).
 11. Females of childbearing potential must not be pregnant or breast-feeding. Male and female patients of reproductive potential must agree to use *two forms* of highly effective contraception from the screening visit through 28 days after the

last dose of study drug unless patient is practicing true abstinence. Acceptable forms of effective contraception include:

- Oral, injected or implanted hormonal methods of contraception.
- Tubal ligation
- Placement of an intrauterine device (IUD) or intrauterine system (IUS).
- Barrier methods of contraception: Condom or Occlusive cap (diaphragm or cervical/vault caps) with spermicidal foam/gel/film/cream/suppository.
- Male sterilization (defined as complete retrograde ejaculation or the appropriate post-vasectomy documentation of the absence of sperm in the ejaculate).
- True abstinence: When this is in line with the preferred and usual lifestyle of the subject. [Periodic abstinence (e.g., calendar, ovulation, symptothermal, post-ovulation methods) and withdrawal are not acceptable methods of contraception.]

Pregnancy tests for females of childbearing potential are required; must be serum at screening and the post treatment safety assessment visit. A positive urine pregnancy test must be confirmed by a serum pregnancy test and a pelvic US since some NSGCT may secrete beta-hCG and cause a false positive pregnancy. A pelvic US does not need to be repeated with each cycle unless the treating physician thinks it is necessary to do so.

12. Potential subject must have the ability to understand (as judged by the treating physician) and willingness to provide written informed consent and HIPAA authorization for release of personal health information.

NOTE: HIPAA authorization may be included in the informed consent or obtained separately. Written informed consent must be obtained from a potential subject prior to the conduct of any study-specific procedures.

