9. CRITERIA FOR DISEASE EVALUATION

Patients will be assessed every cycle by physical examination for response for disease progression and by serum AFP and beta-hCG. Patients will have appropriate radiographic diagnostic procedures (CT scan of chest, abdomen and pelvis) for evaluation of measurable disease at baseline within 28 days of initiation of the study. Imaging can be repeated if required to evaluate the disease (i.e. no elevation of serum tumor markers) before cycle 3, 5 and then every 4 cycles thereafter, at completion of treatment or as clinically indicated. Patients with stable disease or partial or complete response will be eligible for continued therapy.

9.1 The Response Evaluation Criteria in Solid Tumors (RECIST 1.1) will be used as follows:

9.1.1 Measurable disease:

Lesions that can be accurately measured in at least one dimension with longest diameter ≥ 20 mm using conventional techniques or ≥ 10 mm with spiral CT scan.

9.1.2 Malignant lymph nodes:

To be considered pathologically enlarged and measurable, a lymph node must be

>15 mm in short axis when assessed by CT scan (CT scan slice thickness recommended to be no greater than 5 mm). At baseline and in follow-up, only the short axis will be measured and followed.

9.1.3 Non-measurable disease:

All other lesions (or sites of disease), including small lesions (longest diameter

<10 mm or pathological lymph nodes with ≥ 10 to <15 mm short axis), are considered non-measurable disease. Bone lesions, leptomeningeal disease, ascites, pleural/pericardial effusions, lymphangitis cutis/pulmonis, inflammatory breast disease, and abdominal masses (not confirmed and followed by CT or MRI), are considered non-measurable.

Note: Cystic lesions that meet the criteria for radiographically defined simple cysts should not be considered as malignant lesions (neither measurable nor non-measurable) since they are, by definition, simple cysts.

'Cystic lesions' thought to represent cystic metastases can be considered as measurable lesions, if they meet the definition of measurability described above. However, if non-cystic lesions are present in the same patient, these are preferred for selection as target lesions.

9.2 Methods for Evaluation of Measurable Disease:

All measurements should be taken and recorded in metric notation, using a ruler or calipers. All baseline evaluations should be performed within 28 days before the beginning of the treatment.

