12.2 Endpoints

12.2.1 Definition of Primary Endpoint

Objective response rate is the proportion of patients who achieve either a partial or complete response

Complete response is defined as disappearance of all target lesions and normalization of serum tumor markers (AFP and beta-hCG) for at least 4 weeks. Any pathological lymph nodes (whether target or non-target) must have reduction in short axis to <10 mm.

Complete Response must be confirmed four or more weeks after initial CR is observed. In patients whose only evidence of disease is elevated serum tumor markers (AFP or beta-hCG), then values must fall below the upper limit of normal for the assay employed and remain at that level for at least 4 weeks.

Partial response is defined as at least a 30% decrease in the sum of the diameters of target lesions, taking as reference the baseline sum diameters. This should be present on at least 2 measurements 1 month apart. The serum tumor markers (AFP and beta-hCG) should be stable or decreasing. Partial Response must be confirmed four or more weeks after initial PR is observed.

In patients whose only evidence of disease is elevated serum tumor markers (AFP or beta-hCG), then values must fall $\geq 90\%$ below baseline pretreatment levels for beta-hCG or 50% decrease below baseline pretreatment levels for AFP and persist for 6 weeks. If both tumor markers are elevated and one falls below 90% the other should fall at least below 50% of baseline pretreatment levels.

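### Section 3.1 item 4 drops the synopsis requirement for measurable disease or rising markers, and Sections 2.2.1, 9.5 and 12.2.1 differ on who may respond by markers

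*Combined protocol and SAP*

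**What the plan says.** **Eligibility.** Synopsis inclusion item 4 takes "Patients with measurable disease according to RECIST v1.1, or with rising AFP or BHCG above the upper limit of normal" on two consecutive determinations, the marker option being for patients with no measurable radiologic disease. Section 3.1 item 4 reads "Patients must have evidence of recurrent or metastatic carcinoma by one or more of the following", and its first option is "The appearance of metastatic disease by standard imaging techniques". The second option is a rising marker. Nothing else in 3.1 or 3.2 demands measurable disease. Item 3 mentions measurable masses only in one of three alternative definitions of prior treatment failure.

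**Non-measurable disease.** Section 9.1.3 names, among others, "Bone lesions, leptomeningeal disease, ascites, pleural/pericardial effusions, lymphangitis cutis/pulmonis", along with lesions under 10 mm and nodes of 10 to under 15 mm.

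**Response.** Section 12.2.1 (and 9.5) says "Partial response is defined as at least a 30% decrease in the sum of the diameters of target lesions". The marker alternative is introduced by "In patients whose only evidence of disease is elevated serum tumor markers (AFP or beta-hCG"). Section 2.2.1 instead opens marker assessment to patients without measurable disease, and describes them in brackets as marker-only. The non-target criteria in 9.5 allow CR when all non-target lesions disappear and markers are normal.

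**Denominator and rule.** Section 12.4 puts every treated patient in the efficacy population. Section 12.3 closes a cohort at 0 responses in 10 and declares activity at 4 or more in 29.

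**The concern.** The synopsis is stricter than the full criteria, so this is not mere abbreviation, and two sites could rule differently on the same patient. The patients whom only 3.1 admits are ones for whom the endpoint was not written: 2.2.1 divides patients into measurable and marker-only, as if no one fell between. They cannot have a PR but still fill places in a rule that turns on one response at stage 1 and four at the end.

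The second inconsistency concerns patients whom both eligibility texts admit, those with non-measurable lesions and rising markers. Whether a marker fall makes such a patient a responder depends on which section the assessor opens. With thresholds of 1 and 4 responses, one reclassified patient can close a cohort or reverse its conclusion.

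**Working it through.** **Step 1: follow two patients through the text.**

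| | Bone lesions only, normal markers | Bone lesions only, rising markers |
|---|---|---|
| Synopsis item 4 | Not eligible | Eligible |
| 3.1 item 4 | Eligible (imaging option) | Eligible |
| PR by lesion size (9.5, 12.2.1) | No: target lesions are chosen from measurable lesions (9.3) | No |
| PR by markers, 9.5 and 12.2.1 | No | No: markers are not the only evidence of disease |
| PR by markers, 2.2.1 | No: nothing elevated to fall | Arguably yes: no measurable disease |
| CR by non-target criteria, 9.5 | Possible | Possible |
| In efficacy population, 12.4 | Yes | Yes |

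The combination table in 9.6 has no row for a patient without target lesions. Section 12.6 (at least one cycle and a re-evaluation) would not remove either patient.

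**Step 2: reproduce the stated design.** Inputs from 12.3: n1 = 10, stop at 0; n = 29, active at 4 or more; rates 0.05 and 0.20.

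- Early termination under the null: 0.95^10 = 0.5987 (stated 0.599).
- Probability of declaring activity = Σ over x = 1..10 of P(Bin(10, p) = x) × P(Bin(19, p) ≥ 4 − x).
- At p = 0.20: x = 1 gives 0.2684 × 0.7631 = 0.2048; x = 2 gives 0.3020 × 0.9171 = 0.2770; x = 3 gives 0.2013 × 0.9856 = 0.1984; x ≥ 4 gives 0.1209. The sum is 0.8011 (stated 0.801).
- At p = 0.05 the same sum is 0.0468 (stated 0.047).

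**Step 3: illustrate the loss.** Let m of 29 patients have non-measurable disease and normal markers. Both m and their CR rate c are assumptions. The other 29 − m respond at 0.20. The m patients fall at random between the stages, with k in stage 1 with probability C(10,k)·C(19,m−k)/C(29,m). The Step 2 sum is applied for each k, with the m patients responding at rate c.

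For m = 1 and c = 0, power is 0.7667 if the patient is in stage 1 and 0.7862 if in stage 2, so (10 × 0.7667 + 19 × 0.7862)/29 = 0.7795.

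| m | Cohort ORR when c = 0: 0.20 × (29 − m)/29 | Power, c = 0 | Power, c = 0.05 |
|---|---|---|---|
| 0 | 20.0% | 0.8011 | 0.8011 |
| 1 | 19.3% | 0.7795 | 0.7849 |
| 2 | 18.6% | 0.7558 | 0.7675 |
| 3 | 17.9% | 0.7300 | 0.7490 |
| 5 | 16.6% | 0.6717 | 0.7082 |

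**Step 4: hold the cohort rate at 20% instead.** With c = 0, the others must then respond at 0.20 × 29/(29 − m), which is 20.7%, 21.5%, 22.3% or 24.2%. Power is 0.802, 0.803, 0.804 or 0.807, so nothing is lost.

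**The case against.** The strongest reply is that the numerical harm is unproven, and most of that stands.

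- A reader might infer that these patients cannot respond at all. The documents do not support that, because 9.5 leaves CR open through the non-target criteria. The c = 0 column is a worst case.
- A reader might infer that power is lost at a true response rate of 20%. Section 12.3 states its hypotheses for each cohort as a whole, and at a whole-cohort rate of 20% power stays near 0.80. The loss appears only if the 20% was meant for patients who can reach PR; the plan does not say.
- The affected group is narrower than the imaging option suggests. Item 3 also requires failure of prior therapy by growth of measurable masses, new tumors or a marker rise. A marker-normal patient with only an effusion does not clearly meet that. One with new bone lesions could.
- A reader might infer that patients with non-measurable lesions and elevated markers have no PR route anywhere. Section 2.2.1 can be read the other way, so what stands is a disagreement between sections. It does not stem from 3.1 item 4, since the synopsis admits these patients too.

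None of this removes the textual conflicts, which do not depend on frequency.

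**Conclusion.** Two linked inconsistencies stand and should be corrected. First, 3.1 item 4 admits patients with non-measurable, marker-normal disease whom the synopsis excludes. They can respond only by CR and still count in the decision rule. Second, 2.2.1 on one side and 9.5 with 12.2.1 on the other can classify the same patient with non-measurable lesions and elevated markers differently on the primary endpoint.

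The size of the first is modest and conditional. For 1 to 5 such patients in 29, power is 0.78 to 0.67 at worst, or 0.785 to 0.708 at an assumed 5% CR rate, provided the others respond at 20%. It is unchanged if 20% describes the whole cohort. The counts and the CR rate are assumptions. The effect of the second inconsistency cannot be sized from the documents.

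**What to change.** 1. Reconcile 3.1 item 4 with synopsis item 4, so that every enrolled patient has either RECIST-measurable disease or rising markers.
2. Use one definition of the marker-response population in 2.2.1, 9.5 and 12.2.1, and state whether a patient with non-measurable lesions and elevated markers belongs to it.
3. If such patients are included, say how non-target status combines with the marker change (for example, no non-target progression and no new lesions alongside the required fall), and add rows to the 9.6 table for patients without target lesions.

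This is a wording amendment, with no change to sample size, decision rule or assessment schedule. The cost is that a few patients with non-measurable, marker-negative disease become ineligible.
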